Arm ^a	Subject No.	Visit	Date	Time	Temp. (°F)	Systolic Blood Pressure (mmHg)		Diastolic Blood Pressure (mmHg)		Heart Rate (bpm)	Respirations per Minute
						Pressure	Pressure	Pressure	Rate		
xxxxxx	xxxx	xxxxxxxx	xxxxxxxx	xxxxx	xxx	xxx	xxx	xxx	xxx	xxx	xxx
					xxxxx	xxx	xxx	xxx	xxx		
					xxxxx	xxx	xxx	xxx	xxx		
xxxxxx	xxxx	xxxxxxxx	xxxxxxxx	xxxxx	xxx	xxx	xxx	xxx	xxx	xxx	xxx
					xxxxx	xxx	xxx	xxx	xxx		
					xxxxx	xxx	xxx	xxx	xxx		

^a HC = Healthy Control, RA-2 = Rheumatoid Arthritis (stable treatment regimen), RA-3 = Rheumatoid Arthritis (candidate for changed treatment).

STATKING Clinical Services (DD-MMM-YYYY)

Source Program: xxxxxxx.sas

Page x of y

Data Listing 23. ECG Parameters Data Listing
Navidea Biopharmaceuticals - Study No. NAV3-31
Safety Population (N=xxx)

Arm ^a	Subject No.	Visit	Date	Time	Heart Rate (bpm)	PR Interval (msec)	QRS Interval (msec)	QT Interval (msec)	QTcF Interval (msec)	Overall Interpretation
xxxxxx	xxxx	xxxxxx	xxxxx	xxxxxx	xxxxxx	xxxxxxxx	xxxxxxxx	xxxxxx	xxxx	xxxxxxxxxxxxxxxx

^a HC = Healthy Control, RA-2 = Rheumatoid Arthritis (stable treatment regimen), RA-3 = Rheumatoid Arthritis (candidate for changed treatment).

STATKING Clinical Services (DD-MMM-YYYY)

Source Program: xxxxxxxx.sas

Page x of y

Data Listing 24. Study Drug Administration Data Listing
Navidea Biopharmaceuticals - Study No. NAV3-31
Safety Population (N=xxx)

Arm ^a	Subject No.	Date/ Time of Injection	Anatomic Location of Injection	Pre-Injection Radioactivity (mCi)/Time of Measurement	Post- Injection Radioactivity (mCi)/Time of Measurement	Calculated Administered Radioactivity (mCi)	Calculated Mass Dose (µg)	Volume Injected (mL)	Lot Number
xxxxxx	xxxx	xxxxxxxx/xxxx	xxxxxxxx	xxx/xxxx	xxx/xxxx	xxx	xxx	xxx	xxx
xxxxxx	xxxx	xxxxxxxx/xxxx	xxxxxxxx	xxx/xxxx	xxx/xxxx	xxx	xxx	xxx	xxx
		xxxxxxxx/xxxx	xxxxxxxx	xxx/xxxx	xxx/xxxx	xxx	xxx	xxx	xxx

^a HC = Healthy Control, RA-2 = Rheumatoid Arthritis (stable treatment regimen), RA-3 = Rheumatoid Arthritis (candidate for changed treatment).

STATKING Clinical Services (DD-MMM-YYYY)

Source Program: xxxxxxxx.sas

Data Listing 25. Post-Injection Imaging Data Listing
Navidea Biopharmaceuticals - Study No. NAV3-31
Safety Population (N=xxx)

Arm ^a	Subject No.	Visit	Date of Imaging	Start Time of Imaging	SPECT/CT Image Finding
xxxxxx	xxxx	xxxxxxxx	xxxxxx	xx:xx	xxx
xxxxxx	xxxx	xxxxxxxx	xxxxxx	xx:xx	xxx

^a HC = Healthy Control, RA-2 = Rheumatoid Arthritis (stable treatment regimen), RA-3 = Rheumatoid Arthritis (candidate for changed treatment).

^b SPECT/CT imaging performed only in study arm RA-2.

STATKING Clinical Services (DD-MMM-YYYY)

Source Program: xxxxxxx.sas

Page x of y

Data Listing 26. SPECT/CT Reader Results Data Listing - Hands and Wrists
Navidea Biopharmaceuticals - Study No. NAV3-31
Safety Population (N=xxx)

Arm ^a	Subject No.	Post-Injection Imaging Time Point	Joint	SPECT/CT Image Finding
xxxxxx	xxxx	xxxxxxxx	xxxxxxxxxxxx	xxxx
xxxxxx	xxxx	xxxxxxxx	xxxxxxxxxxxx	xxxx

^a HC = Healthy Control, RA-2 = Rheumatoid Arthritis (stable treatment regimen), RA-3 = Rheumatoid Arthritis (candidate for changed treatment).

STATKING Clinical Services (DD-MMM-YYYY)
Source Program: xxxxxxx.sas

Page x of y

Data Listing 27. TUV Data Listing
 Navidea Biopharmaceuticals - Study No. NAV3-31
 Safety Population (N=xxx)

TUV Classification of Improvement								
Arm ^a	Subject No.	Algorithms Predicting Improvement ^b	Algorithms Predicting No Improvement ^b	Reader No.	Visit	Date/Time	Region of Interest ^c	TUV
xxxxxx	xxxx	x, x, x	x, x, x, x	xxx	xxxxxx	xxxxxx	xxxxxx	xxxxxx
				xxx	xxxxxx	xxxxxx	xxxxxx	xxxxxx
				xxx	xxxxxx	xxxxxx	xxxxxx	xxxxxx
				xxx	xxxxxx	xxxxxx	xxxxxx	xxxxxx
				xxx	xxxxxx	xxxxxx	xxxxxx	xxxxxx
xxxxxx	xxxx	x	x, x, x, x, x, x	xxx	xxxxxx	xxxxxx	xxxxxx	xxxxxx

^a HC = Healthy Control, RA-2 = Rheumatoid Arthritis (stable treatment regimen), RA-3 = Rheumatoid Arthritis (candidate for changed treatment).

^b 1 = Change in Global TUV(5w) Bucketing, 2 = Change in Global TUV(5w), 3 = Change in Global TUV(5w) Bucketing with ACPA Bucketing, 4 = Change in Global TUV(12w) Bucketing, 5 = Change in Global TUV(12w), 6 = Change in Global TUV(12w) Bucketing with ACPA Bucketing, 7 = ACPA Bucketing Alone.

^c Region of Interest is joint for all arms, and joint or Global for the RA-2 and RA-3 arms.

STATKING Clinical Services (DD-MMM-YYYY)

Source Program: xxxxxxx.sas

Page x of y

Data Listing 28. ACR Response Criteria Data Listing
Navidea Biopharmaceuticals - Study No. NAV3-31
Safety Population (N=xxx)

Arm ^a	Subject No.	Visit	ACR Response Assessment ^b	Number of Tender Joints	Number of Swollen Joints	Patient Global Assessment	Physician Global Assessment	HAQ Total	VAS Pain Score	ESR
xxxxxx	xxxx	xxxxxx	xxxxx	xxx	xxx	xxx	xxx	xxx	xxx	xxx
xxxxxx	xxxx	xxxxxx	xxxxx	xxx	xxx	xxx	xxx	xxx	xxx	xxx

^a HC = Healthy Control, RA-2 = Rheumatoid Arthritis (stable treatment regimen), RA-3 = Rheumatoid Arthritis (candidate for changed treatment).

^b Response assessment will be blank for baseline measurements.

STATKING Clinical Services (DD-MMM-YYYY)

Source Program: xxxxxxxx.sas

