1.3 Sample Size

Up to 105 subjects from up to 10 study centers will be enrolled into Arms 1, 2, and 3 as allocated below, and imaged. Arm 1 will have N = 38 evaluable subjects, Arm 2 will have N = 38 evaluable subjects, and Arm 3 will have N = 29 evaluable subjects. A subject is considered evaluable if he/she meets the criteria for the analysis population and has the data necessary for computing the primary endpoint.

The sample size for Arm 1 was determined to assess temporal stability of the 150 μ g mass dose/10mCi radiolabeling dose. The sample size for Arm 2 was determined to power a hypothesis test at 0.80:

$$\begin{aligned} H_0: \pi &\leq 0.80 \\ &\text{vs} \\ H_a: \pi &> 0.80, \end{aligned}$$

where π represent the fraction of unsigned differences less than 7.5% The sample size for Arm 3 was determined to provide a lower 97.5% confidence limit for the rank correlation of at most 0.15 when $\rho = 0.70$, using Fisher's Z-transformation methods.

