Each subject will be classified as a yes or a no for whether they meet each of the above ACR Response Criteria at each of the applicable post-baseline time points. Note that the above criteria are nested, such that if a subject is a yes for ACR70 at a given time point, then the subject is also a yes for ACR50 and ACR20 for that same time point.

A subject will be classified as improved on the CDAL depending on the baseline score as follows:

- If the baseline value is greater than 22, a reduction of more than 12 will be classified as improved. Otherwise, the subject is not improved.

- If the baseline value is between 10 and 22 (inclusive) a decrease of more than 6 will classified as improved. Otherwise, the subject is not improved.
- If the baseline value is less than 10, a decrease of more than 1 will be classified as improved. Otherwise the subject is not improved.

A subject will be classified as improved on the DAS28 with a score change of greater than 1.2.

A decrease of at least 0.22 in the HAQ-DI will be classified as improved. Otherwise, the subject is not improved on the HAQ-DI.

The $\Delta TUV_{global[5w]}$ values will be used to predict improvement at 12 and 24 weeks according to algorithms 1-3. The $\Delta TUV_{global[12w]}$ values will be used to predict improvement at 24 weeks according to algorithms 4-6. A seventh algorithm based on ACPA bucketing alone will also be applied to predict improvement at 12 and 24 weeks. Algorithms 1-6 will be applied after the change in TUV calculations have been rounded to the nearest integer percentage (i.e., nearest hundredths place for a proportion).

1. $\Delta TUV_{global[5w]}$ bucketing

In the below, TUV_{global} represents the global TUV at the current time point and $TUV_{global[Day 0]}$ represents the global TUV at baseline:

- If $TUV_{global[Day 0]}$ is < 5 then the prediction is N (No improvement)
- Else if

$$\Delta TUV_{global[5w]} = \frac{TUV_{global[5w]} - TUV_{global[Day 0]}}{TUV_{global[Day 0]}} \leq -0.10$$

the prediction is Y (patient has improved). That is, a patient will be predicted as improved if TUV_{global} goes down by greater than or equal to 10%.

- Otherwise, the prediction is N.

2. $\Delta TUV_{global[5w]}$

The TUV_{global} prediction of improvement will also be computed according to the following algorithm:

- If TUV_{global} goes down by greater than or equal to 10%, then predict response
- If TUV_{global} does not go down by 10% or more, then predict no response

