 - ACPA levels ≤ 85 predicts treatment failure (non-response)
 - ACPA level >85 predicts treatment success (significant clinical improvement)

7. ACPA bucketing alone

The following will be used to predict improvement solely on the basis of ACPA:

- ACPA baseline level ≤ 85 predicts treatment failure (non-response)
- ACPA baseline level >85 predicts treatment success (significant clinical improvement)

For each of the RA improvement criteria, a cross-classification table will be provided. The Uncertainty coefficient for the clinical criterion given the $\Delta TUV_{\text{global}[5w]}$ of $\Delta TUV_{\text{global}[12w]}$ classification and its standard error will be calculated. The positive predictive value (PPV), negative predictive value (NPV), and overall accuracy (OA) will be calculated and 95% exact (Clopper-Pearson) confidence intervals will be provided.

PPV and NPV will be calculated as follows, where $\Delta TUV_{\text{global}[XXw]}$ is either $\Delta TUV_{\text{global}[5w]}$ or $\Delta TUV_{\text{global}[12w]}$, as appropriate:

Clinical Criterion Classification			
$\Delta TUV_{global[XXw]}$ and/or ACPA Classification	Improved	Not Improved	Total
Improved	A	B	A+B
Not Improved	C	D	C+D
Total	A+C	B+D	A+B+C+D

$$PPV = A/(A+B)$$

$$NPV = D/(C+D)$$

$$OA = (A+D)/(A+B+C+D).$$

A separate table will be provided to summarize the baseline ACPA levels on a continuous scale and the number and percentage of subjects in each ACPA category (≤ 70 , > 70).

Figures displaying the ΔTUV_{global} by time point (5, 12, and 24 weeks) will be created to display the relationship between ΔTUV_{global} over time with the corresponding clinical response assessment (ACR20/50/70, DAS28, and CDAI) at the given time point.

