^a HC = healthy control, RA-2 = rheumatoid arthritis (stable treatment regimen), RA-3 = rheumatoid arthritis (candidate for changed treatment).

^b RAW = data recorded in database; CFB = change from baseline= (parameter value at the current time point)-(Baseline parameter value).
 STATKING Clinical Services (DD-MMM-YYYY)

Source Program: xxxxxxx.sas

Table 42. ACR Response Classification by Time Point
Navidea Biopharmaceuticals - Study No. NAV3-31
ITD Population (N=xxx)

Arm 3 - RA-3^a Subjects Only

Time Point	Assessment			
	ACR-0	ACR-20	ACR-50	ACR-70
Week 5	xxx (xxx%)	xxx (xxx%)	xxx (xxx%)	xxx (xxx%)
Week 12	xxx (xxx%)	xxx (xxx%)	xxx (xxx%)	xxx (xxx%)
Week 24	xxx (xxx%)	xxx (xxx%)	xxx (xxx%)	xxx (xxx%)

^a HC = Healthy Control, RA-2 = Rheumatoid Arthritis (stable treatment regimen), RA-3 = Rheumatoid Arthritis (candidate for changed treatment).

STATKING Clinical Services (DD-MMM-YYYY)

Source Program: xxxxxxx.sas

Table Format Repeats for PP Population.

Table 44. Concordance of $\Delta\text{TUV}_{\text{global}[5w]}$ Bucketing and Week 12 Clinical Improvement Criteria
 Navidea Biopharmaceuticals - Study No. NAV3-31
 ITD Population (N=xxx)

Arm 3 - RA-3^a Subjects Only

Part 1 of 6: ACR-20

ATUV _{global[5w]} Classification	Clinical Assessment			Measure	Value ^b
	Improved	Not Improved	Total		
Improved	xxx (xxx%)	xxx (xxx%)	xxx (xxx%)	Uncertainty Coefficient (C R)	xxxx (xxxxx)
Not Improved	xxx (xxx%)	xxx (xxx%)	xxx (xxx%)	Uncertainty Coefficient (Symmetric)	xxxx (xxxxx)
Total	xxx (xxx%)	xxx (xxx%)	xxx (xxx%)	Positive Predictive Value Confidence Limits	xxxx (xxxx, xxxx)
				Negative Predictive Value Confidence Limits	xxxx (xxxx, xxxx)
				Overall Accuracy Confidence Limits	xxxx (xxxx, xxxx)

^a HC = Healthy Control, RA-2 = Rheumatoid Arthritis (stable treatment regimen), RA-3 = Rheumatoid Arthritis (candidate for changed treatment).

^b Values in parentheses are standard errors for the uncertainty coefficients, and p-values for positive predictive value and negative predictive value testing $H_0: \pi = 0.6$.

STATKING Clinical Services (DD-MMM-YYYY)

Source Program: xxxxxxx.sas

This part repeats for Part 2 (ACR-50), Part 3 (ACR-70), Part 4 (CDAI), Part 5 (DAS28), and Part 6 (HAQ-DI)
Full table format repeats for PP population (table 45) and for tables 46 - 65.

[figure not shown]
Table 66. ACPA Summary Statistics in Arm 3
Navidea Biopharmaceuticals - Study No. NAV3-31
ITD Population (N=xxx)

Visit	Variable or Category ^a	Statistic	ITD Population (N=xxx)

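### The concordance tables test PPV and NPV against one unexplained value, 0.6, so their p-values do not show whether TUV or ACPA predicts response

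*SAP*

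**What the plan says.** SAP section 4.2.2 defines seven algorithms that classify each Arm 3 subject as predicted improved or not, from the change in global TUV, from baseline ACPA, or from both. Each is cross-classified against ACR20, ACR50, ACR70, CDAI, DAS28 and HAQ-DI improvement. With cells A, B, C and D, PPV is A/(A+B) and NPV is D/(C+D). The planned output is the uncertainty coefficient with its standard error, then PPV, NPV and accuracy: "overall accuracy (OA) will be calculated and 95% exact (Clopper-Pearson) confidence intervals will be provided". The section names no hypothesis test and no null value for PPV or NPV.

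The Table 44 shell in Appendix B adds one. Footnote b says the bracketed values are standard errors for the uncertainty coefficients and "p-values for positive predictive value and negative predictive value testing" a null of pi = 0.6. The shell is repeated for the other five criteria, and "Full table format repeats for PP population (table 45) and for tables 46 - 65". In the shell itself, the PPV and NPV rows are labelled as confidence limits and hold a pair of values in brackets. There is no field for a p-value.

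On the three ACR levels, section 4.2.2 says: "Note that the above criteria are nested". On size, section 1.3 says: "Arm 3 will have N = 29 evaluable subjects". That number was set for the rank correlation, not for PPV or NPV.

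**The concern.** PPV and NPV depend on how common the response is. If the prediction is independent of the outcome, the expected PPV is the response rate and the expected NPV is one minus it. A test against chance must therefore use a different null for PPV than for NPV, and a different null for each criterion. Because the ACR levels are nested, the ACR20 rate is at least the ACR50 rate, which is at least the ACR70 rate. A single 0.6 cannot be the chance level for all three unless the rates coincide.

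The footnote covers 22 tables (44 to 65) x 6 criteria x 2 measures = 264 p-values, half of them in the ITD population. A reader of the study report would naturally take a small one as evidence that the algorithm works. For a rare criterion a small NPV p-value can arise from rarity alone, and for a common criterion the same holds for PPV. SAP Table 1 names PPV and NPV among the Arm 3 evaluations, so these cells will be looked at.

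**Working it through.** **Nothing to reproduce.** No derivation, power, alpha or sidedness is attached to 0.6 in either document.

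**Inputs from the SAP.** N = 29 (section 1.3); the PPV and NPV definitions (section 4.2.2); null 0.6 for both measures (Table 44, footnote b).

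**Assumptions.** Response rates r from 0.2 to 0.8; 10 or 15 of the 29 predicted improved, leaving 19 or 14 predicted not improved; exact binomial test at 0.05, both two-sided and one-sided.

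**Step 1: counts needed for significance above 0.6.**

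| Subjects in the row | Two-sided | One-sided |
|---|---|---|
| 10 | 10 | 9 |
| 14 | 13 | 12 |
| 15 | 13 | 13 |
| 19 | 16 | 16 |

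**Step 2: useless predictor.** Correct calls among those predicted improved follow Bin(m, r). Among those predicted not improved they follow Bin(m, 1 - r).

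NPV at r = 0.2:
- m = 19: P(Bin(19, 0.8) >= 16) = 0.455, either sidedness.
- m = 14: P(Bin(14, 0.8) >= 13) = 0.198 two-sided; P(Bin(14, 0.8) >= 12) = 0.448 one-sided.

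PPV at r = 0.8:
- m = 10: 0.8^10 = 0.107 two-sided; P(Bin(10, 0.8) >= 9) = 0.376 one-sided.
- m = 15: P(Bin(15, 0.8) >= 13) = 0.398, either sidedness.

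At r = 0.4, 0.5 and 0.6, the chance that either measure is significantly above 0.6 is at most 0.027 two-sided and 0.046 one-sided.

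**Step 3: comparator.** One-sided Fisher's exact test on the same 2x2 tables, enumerated for a useless predictor, rejects with probability 0.008 to 0.021 at r = 0.2 and 0.8. It stays at or below 0.031 for r between 0.1 and 0.9.

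**Step 4: two example tables (A, B, C, D), two-sided p-values.**
- (2, 12, 2, 13): odds ratio (2 x 13)/(12 x 2) = 1.08, Fisher p = 1.00. NPV is 13/15 = 0.87, with p = 0.036 against 0.6.
- (11, 4, 4, 10): odds ratio (11 x 10)/(4 x 4) = 6.9, Fisher p = 0.027. PPV is 11/15 and NPV is 10/14, each with p = 0.43 against 0.6.

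The first table shows no association but a significant NPV. The second shows a clear association but neither p-value is significant.

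**The case against.** A fixed minimum predictive value is a legitimate kind of goal, and 0.6 may have been meant as one. If so, a non-significant PPV is not an error. With sensitivity 0.8 and specificity 0.7 at 20% response, true PPV is 0.16/(0.16 + 0.24) = 0.40, and a test against 0.6 should not reject. The same predictor has true NPV 0.56/(0.56 + 0.04) = 0.93, and its NPV test is significant in about 94% of simulated trials one-sided. A reader might infer that the 0.6 test fails to detect an informative predictor. It does not fail at its own question, which is a threshold question and not one of association. This stands, but neither document states such a goal or gives a reason for 0.6.

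A reader might also infer that the p-value depends only on the response rate. It depends as well on the prediction split and on sensitivity and specificity. The 20-46% range above comes from the split alone.

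Reading PPV and NPV together protects to some extent. For a useless predictor the two true values sum to 1, so both cannot exceed 0.6, and in the enumeration both were significant in fewer than 1 in 10,000 trials. But each p-value is presented separately, and nothing in the SAP says that both are required.

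Nor is the plan without a measure of association. The uncertainty coefficient is zero under independence, and the shell prints the margins, so the response rate is visible. The coefficient carries only a standard error, however, so the only p-values in the block answer a different question.

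Finally, the p-values may never be produced, since section 4.2.2 and the shell cells call for confidence limits. The inconsistency still has to be settled before programming.

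**Conclusion.** The point holds with limited weight. Footnote b tests PPV and NPV for six criteria against one unexplained value that the SAP text does not mention and the shell cells cannot hold. Those p-values do not show whether TUV or ACPA predicts response.

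The size depends on assumed response rates and splits. A useless predictor's NPV is significant in 20-46% of trials two-sided (about 45% one-sided) at 20% response. Its PPV is significant in 11-40% two-sided (38-40% one-sided) at 80% response. Near 50% response the problem is small.

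A reader might infer that the trial's conclusions are at risk. The documents do not support that: these are secondary analyses, with no success criterion or decision rule attached to the p-values.

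**What to change.** Remove the pi = 0.6 p-values from footnote b. In their place give one Fisher's exact test of association per 2x2 table, with its sidedness stated, labelled descriptive and unadjusted. That is 22 x 6 = 132 p-values instead of 264. Name the test in section 4.2.2 so that the text, shell and footnote agree.

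Print PPV beside the observed response rate and NPV beside the observed non-response rate. Keep the Clopper-Pearson intervals and the uncertainty coefficient.

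If 0.6 is meant as a performance goal, say so, justify it for each criterion, and show that comparison in addition to the test against chance.

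The cost is a footnote, a sentence in section 4.2.2 and minor reprogramming of secondary tables. No further data are needed.

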3. $\Delta TUV_{global[5w]}$ bucketing with ACPA bucketing

The TUV_{global} prediction of improvement will also be evaluated by combination of the above two algorithms such that:

For patients with TUV_{global} of below 5.0 at baseline:

- ACPA Levels before initiation (at baseline) of the new anti-TNF therapy:
 - ACPA levels ≤ 85 predicts treatment failure (non-response)
 - ACPA level >85 predicts treatment success (significant clinical improvement)

For patients with TUV_{global} at or above 5.0 at baseline:

- If TUV_{global} goes down by greater than or equal to 10%, then predict response (no need to refer to ACPA)
- If TUV_{global} does not go down by 10% or more, then refer to baseline ACPA for prediction:
 - ACPA levels ≤ 85 predicts treatment failure (non-response)
 - ACPA level >85 predicts treatment success (significant clinical improvement)

4. $\Delta TUV_{global[12w]}$ bucketing

In the below, TUV_{global} represents the global TUV at the current time point and $TUV_{global[Day 0]}$ represents the global TUV at baseline:

- If $TUV_{global[Day 0]}$ is < 5 then the prediction is N (No improvement)
- Else if

$$\Delta TUV_{global[12w]} = \frac{TUV_{global[12w]} - TUV_{global[Day 0]}}{TUV_{global[Day 0]}} \leq -0.10$$

the prediction is Y (patient has improved). That is, a patient will be predicted as improved if TUV_{global} goes down by greater than or equal to 10%.

- Otherwise, the prediction is N.

5. $\Delta TUV_{global[12w]}$

The TUV_{global} prediction of improvement will also be computed according to the following algorithm:

- If TUV_{global} goes down by greater than or equal to 10%, then predict response
- If TUV_{global} does not go down by 10% or more, then predict no response

6. $\Delta TUV_{\text{global}[12w]}$ bucketing with ACPA bucketing

The TUV_{global} prediction of improvement will also be evaluated by combination of the above two algorithms such that:

For patients with TUV_{global} of below 5.0 at baseline:

- ACPA Levels before initiation (at baseline) of the new anti-TNF therapy:
 - ACPA levels ≤ 85 predicts treatment failure (non-response)
 - ACPA level >85 predicts treatment success (significant clinical improvement)

For patients with TUV_{global} at or above 5.0 at baseline:

- If TUV_{global} goes down by greater than or equal to 10%, then predict response (no need to refer to ACPA)
- If TUV_{global} does not go down by 10% or more, then refer to baseline ACPA for prediction:

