52	Concordance of $\Delta TUV_{global[5w]}$ Bucketing with ACPA Bucketing and Week 12 Clinical Improvement Criteria (ITD Population)	X	
53	Concordance of $\Delta TUV_{global[5w]}$ Bucketing with ACPA Bucketing and Week 12 Clinical Improvement Criteria (PP Population)	X	
54	Concordance of $\Delta TUV_{global[5w]}$ Bucketing with ACPA Bucketing and Week 24 Clinical Improvement Criteria (ITD Population)	X	
55	Concordance of $\Delta TUV_{global[5w]}$ Bucketing with ACPA Bucketing and Week 24 Clinical Improvement Criteria (PP Population)	X	
56	Concordance of $\Delta TUV_{global[12w]}$ Bucketing and Week 24 Clinical Improvement Criteria (ITD Population)	X	
57	Concordance of $\Delta TUV_{global[12w]}$ Bucketing and Week 24 Clinical Improvement Criteria (PP Population)	X	
58	Concordance of $\Delta TUV_{global[12w]}$ and Week 24 Clinical Improvement Criteria (ITD Population)	X	
59	Concordance of $\Delta TUV_{global[12w]}$ and Week 24 Clinical Improvement Criteria (PP Population)	X	
60	Concordance of $\Delta TUV_{global[12w]}$ Bucketing with ACPA Bucketing and Week 24 Clinical Improvement Criteria (ITD Population)	X	
61	Concordance of $\Delta TUV_{global[12w]}$ Bucketing with ACPA Bucketing and Week 24 Clinical Improvement Criteria (PP Population)	X	
62	Concordance of ACPA Bucketing Alone and Week 12 Clinical Improvement Criteria (ITD Population)	X	
63	Concordance of ACPA Bucketing Alone and Week 12 Clinical Improvement Criteria (PP Population)	X	
64	Concordance of ACPA Bucketing Alone and Week 24 Clinical Improvement Criteria (ITD Population)	X	
65	Concordance of ACPA Bucketing Alone and Week 24 Clinical Improvement Criteria (PP Population)	X	
66	ACPA Summary Statistics in Arm 3 (ITD Population)	X	X
67	ACPA Summary Statistics in Arm 3 (PP Population)	X	

Figure No.	Figure Title	Included in Final Figures	Shown in Appendix B
Fig1	Plot of ΔTUV_{global} by Imaging Time Point and ACR-20 for Arm 3 (ITD Population)	X	X
Fig2	Plot of ΔTUV_{global} by Imaging Time Point and ACR-50 for Arm 3 (ITD Population)	X	
Fig3	Plot of ΔTUV_{global} by Imaging Time Point and ACR-70 for Arm 3 (ITD Population)	X	

Figure No.	Figure Title	Included in Final Figures	Shown in Appendix B
Fig4	Plot of ΔTUV_{global} by Imaging Time Point and CDAI for Arm 3 (ITD Population)	X	
Fig5	Plot of ΔTUV_{global} by Imaging Time Point and DAS28 for Arm 3 (ITD Population)	X	

Listing No.	Data Listing Title	Included in Final Listings	Shown in Appendix B
DL1	Subject Disposition Data Listing	X	X

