Screening (Baseline)	Quantitative ACPA Level	Mean (Std Dev) n Median (Min, Max)	xxx (xxxx) xxx xxx (xxx, xxx)
	ACPA Level ≤ 70	n (%)	xxx (xxx%)
	ACPA Level > 70	n (%)	xxx (xxx%)

^a Categories correspond to the ACPA bucketing levels used in the prediction of improvement algorithms.
STATKING Clinical Services (DD-MMM-YYYY)
Source Program: xxxxxxx.sas

Table format repeats for PP population

Figure 1. Plot of ΔTUV_{global} by Imaging Time Point and ACR-20 for Arm 3
Navidea Biopharmaceuticals - Study No. NAV3-31
ITD Population (N=xxx)

Responder status based on ACR-20 at each week.

STATKING Clinical Services (DD-MMM-YYYY)

Source Program: xxxxxxx.sas

Figure format repeats for Figures 2-5. Footnote text will be updated in each figure to correspond to the clinical assessment noted in the title (ACR-50, ACR-70, CDAI, or DAS28).

Page x of y

Data Listing 1. Subject Disposition Data Listing
Navidea Biopharmaceuticals - Study No. NAV3-31

Arm ^a	Subject No.	Disposition Status	Date of Completion or Withdrawal	Withdrawal Reason
xxxxxx	xxxx	xxxxxxxxxxxxxxxxxxxxxx	xxxxxxxxxx	xxxxxxxxxxxxxxxxxxxxxxxx
xxxxxx	xxxx	xxxxxxxxxxxxxxxxxxxxxx	xxxxxxxxxx	xxxxxxxxxxxxxxxxxxxxxx
xxxxxx	xxxx	xxxxxxxxxxxxxxxxxxxxxx	xxxxxxxxxx	xxxxxxxxxxxxxxxxxxxxxx
xxxxxx	xxxx	xxxxxxxxxxxxxxxxxxxxxx	xxxxxxxxxx	xxxxxxxxxxxxxxxxxxxxxx

^a HC = Healthy Control, RA-2 = Rheumatoid Arthritis (stable treatment regimen), RA-3 = Rheumatoid Arthritis (candidate for changed treatment).

STATKING Clinical Services (DD-MMM-YYYY)

Source Program: xxxxxxx.sas

Page x of y

Data Listing 2. Inclusion/Exclusion Data Listing
 Navidea Biopharmaceuticals - Study No. NAV3-31

Arm ^a	Subject No.	Did Subject Meet All Eligibility Criteria?	Criterion Category	Criterion	Was a Waiver Granted?	Is Subject a Screen Failure?
xxxxxx	xxxx	xxxx	xxxxxxxxxxxxxxxxxxxxxxxxxxxx	xxxxxxxxxx	xxxx	xxxx
xxxxxx	xxxx	xxxx	xxxxxxxxxxxxxxxxxxxxxxxxxxxx	xxxxxxxxxx	xxxx	xxxx
xxxxxx	xxxx	xxxx	xxxxxxxxxxxxxxxxxxxxxxxxxxxx	xxxxxxxxxx	xxxx	xxxx
xxxxxx	xxxx	xxxx	xxxxxxxxxxxxxxxxxxxxxxxxxxxx	xxxxxxxxxx	xxxx	xxxx

^a HC = Healthy Control, RA-2 = Rheumatoid Arthritis (stable treatment regimen), RA-3 = Rheumatoid Arthritis (candidate for changed treatment).
 STATKING Clinical Services (DD-MMM-YYYY)
 Source Program: xxxxxxxx.sas

Page x of y

Data Listing 3. Protocol Deviations Data Listing
Navidea Biopharmaceuticals - Study No. NAV3-31

Arm ^a	Subject No.	Date of Deviation	Deviation Description	Deviation Category (Major/Minor)

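### The SAP gives two baseline ACPA cut-offs: 85 in every prediction rule, but 70 in the summary table whose footnote says the categories are those rules' levels

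*SAP*

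**What the plan says.** SAP Section 4.2.2 defines seven rules that predict clinical improvement in Arm 3. Three of them use baseline ACPA.

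- **Algorithms 3 and 6** (change in global TUV at week 5 and week 12 respectively, combined with ACPA) each contain two ACPA rule pairs. One applies when baseline global TUV is below 5.0. The other applies when it is 5.0 or more but has not fallen by at least 10%. In each pair the lower side reads "ACPA levels ≤ 85 predicts treatment failure (non-response", closing the bracket, and the upper side is above 85.
- **Algorithm 7** (ACPA alone) has one pair: "ACPA baseline level ≤ 85 predicts treatment failure (non-response", closing the bracket, with improvement predicted above 85.

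Later in Section 4.2.2 a separate table is promised, giving the "number and percentage of subjects in each ACPA category (≤ 70" and above 70). The Table 66 shell in Appendix B follows that sentence. Its lower row is "ACPA Level ≤ 70" and its upper row is above 70. Footnote a to that shell says: "Categories correspond to the ACPA bucketing levels used in the prediction of improvement algorithms". The format repeats for the per-protocol version, Table 67.

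**The concern.** A threshold that decides predictions is stated two ways, and a footnote says the two are the same. A programmer who follows the SAP exactly will produce Tables 66-67 at 70 and the concordance tables at 85, with nothing in the output to warn the reader.

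Two things are at stake:

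- **If 85 is intended.** Tables 66-67 misdescribe how many subjects ACPA places on each side of the prediction rule.
- **If 70 is intended.** The predictions themselves are at issue in Tables 52-55 (algorithm 3), 60-61 (algorithm 6) and 62-65 (algorithm 7, for example "Concordance of ACPA Bucketing Alone and Week 12 Clinical Improvement Criteria (ITD Population", closing the bracket). The positive predictive value (PPV), negative predictive value (NPV) and overall accuracy in those tables would follow. Algorithm 7 is also the only rule of the seven that uses no imaging, so its cut-off sets the non-imaging comparison for the TUV rules.

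**Working it through.** **1. The cut-offs side by side**

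| Place in the SAP | ACPA cut-off |
|---|---|
| 4.2.2, algorithm 3, baseline global TUV below 5.0 | 85 |
| 4.2.2, algorithm 3, 5.0 or more without a 10% fall | 85 |
| 4.2.2, algorithm 6, baseline global TUV below 5.0 | 85 |
| 4.2.2, algorithm 6, 5.0 or more without a 10% fall | 85 |
| 4.2.2, algorithm 7 | 85 |
| 4.2.2, sentence on the ACPA summary table | 70 |
| Appendix B, Table 66 (repeated for Table 67) | 70 |

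The rule pairs number 2 + 2 + 1 = 5, all at 85. None uses 70.

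**2. Does anything reconcile them?**

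- The revision history for version 1.0 to 1.1 lists two changes: the 10% rule in algorithms 1 and 4, and the rounding of TUV changes. Neither concerns ACPA.
- The protocol has no ACPA bucketing rule. Its Appendix 5 grades ACPA by multiples of the upper limit of normal, which explains neither number.
- A deliberately separate descriptive split is ruled out by the Table 66 footnote.

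**3. Who is affected?** Only subjects with baseline ACPA above 70 and up to 85. In algorithm 7 every such subject is affected. In algorithms 3 and 6 only those whose prediction falls through to ACPA are affected. A subject with baseline global TUV of 5.0 or more and a fall of at least 10% never reaches it: "then predict response (no need to refer to ACPA", closing the bracket.

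**4. How likely is at least one such subject?** The documents give no ACPA distribution and no units, so the proportion p in this range is an assumption. With the 29 evaluable subjects planned for Arm 3, the chance is 1 − (1 − p)^29:

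| Assumed p | Chance of at least one in 29 |
|---|---|
| 0% | 0% |
| 0.5% | 14% |
| 2% | 44% |
| 5% | 77% |
| 10% | 95% |

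**5. Effect per subject, as written.** Each one shifts the Table 66 counts by one against the row totals of Tables 62 and 64: 1/29 = 3.4%.

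**6. Effect per subject, if 70 was intended.** In algorithm 7 the subject moves from the predicted-not-improved row to the predicted-improved row, and overall accuracy changes by 1/29 = 3.4 points, up or down. Moves in opposite directions cancel.

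The next table is for scale only. It uses an invented 2×2 table of 29 subjects (A = 9, B = 6, C = 5, D = 9, in the SAP's notation) with one subject moved:

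| | Before | Moved subject clinically improved | Moved subject not improved |
|---|---|---|---|
| PPV | 9/15 = 60.0% | 10/16 = 62.5% | 9/16 = 56.3% |
| NPV | 9/14 = 64.3% | 9/13 = 69.2% | 8/13 = 61.5% |
| Overall accuracy | 18/29 = 62.1% | 19/29 = 65.5% | 17/29 = 58.6% |

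With these row sizes, the most that one subject can do is 6.25 points on PPV (15/15 to 15/16, or 0/15 to 1/16) and 7.1 points on NPV (13/14 to 13/13, or 1/14 to 0/13).

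**The case against.** The strongest reply is that the operative rules are not ambiguous. The value 85 stands on both sides of all five rule pairs, while 70 appears only in a descriptive sentence and its shell, which feed no algorithm, test or interval. Read literally, Section 4.2.2 gives one set of predictions, and a stale 70 is the likeliest explanation. Tables 66-67 also report ACPA on a continuous scale, and affected subjects could be traced by hand from Listing 15 (individual ACPA values) and Listing 27 (individual predictions). All of this stands, and it limits the seriousness of the point. It does not make the footnote true.

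The effect on PPV and NPV is conditional on 70 being intended, and the weight of those statistics should not be overstated. The Table 44 shell, repeated for Tables 46-65, has a footnote that mentions "p-values for positive predictive value and negative predictive value testing" a value of 0.6. Section 4.2.2 itself specifies only exact 95% confidence intervals, and no success criterion is attached to 0.6. That qualification also stands.

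The interim analysis plans for the second and third interim analyses are not among the documents, so they may give a basis for one of the values. The revision history covers only the step from version 1.0 to 1.1, so its silence does not show which value was meant. Both remarks are fair, but neither removes the need for the SAP to state a single cut-off.

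**Conclusion.** The contradiction holds on the face of the SAP and needs no inference: five rule pairs at 85, a summary sentence and table shell at 70, and a footnote equating them. It should be fixed, but it is not a threat to the primary analysis.

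The likeliest consequence is a wrong category split and a false footnote in Tables 66-67, with one count misplaced for each subject in the relevant analysis population who lies between the cut-offs. The number of such subjects cannot be derived from the documents; the probabilities above rest entirely on the assumed p and on 29 subjects. Only if 70 was intended do the secondary predictions and their accuracy measures change. The documents do not settle which value was meant.

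**What to change.** Before database lock, reconcile the passages:

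1. State one ACPA cut-off, with its units and basis.
2. Use it in algorithms 3, 6 and 7, in the Section 4.2.2 summary sentence, and in Tables 66 and 67.
3. Add a programmed check, paired by population. The Table 66 counts at or below and above the cut-off should equal the Not Improved and Improved row totals of Tables 62 and 64 (intent-to-diagnose). The Table 67 counts should equal those of Tables 63 and 65 (per-protocol). Subjects missing a clinical criterion are the only allowed difference.

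If the algorithms' value is confirmed, the change is one sentence and one table shell. Otherwise it is the three algorithm definitions (five rule pairs). Neither route needs new data.
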